10.5 APPENDIX 5: GENETICS

Use/Analysis of DNA

- Genetic variation may impact a participant's response to study intervention, susceptibility to, and severity and progression of disease. Variable response to study intervention may be due to genetic determinants that impact drug absorption, distribution, metabolism, and excretion; mechanism of action of the drug; disease etiology; and/or molecular subtype of the disease being treated. Therefore, where local regulations and IRB/IEC allow, a blood sample will be collected for DNA analysis from consenting participants.
- For all participants, a blood sample will be collected for mandatory filaggrin gene sequencing analysis.
- For participants, who consent to optional genetic research, a DNA sample will be stored for broad genetic analysis, which may include, but is not limited to, whole genome or exome sequencing.

- The samples may be analyzed as part of a multi-study assessment of genetic factors involved in the response to dupilumab or study interventions of this class to understand study disease or related conditions.
- The results of genetic analyses may be reported in the clinical study report (CSR) or in a separate study summary.
- The Sponsor will store the DNA samples in a secure storage space with adequate measures to protect confidentiality.
- The samples will be retained while research on dupilumab or study interventions of this class continues but no longer than 15 years or other period as per local requirements.

10.6 APPENDIX 6: COUNTRY-SPECIFIC REQUIREMENTS

Not applicable.

10.7 APPENDIX 7: ABBREVIATIONS

AD:	atopic dermatitis
AE:	adverse event
AESI:	adverse events of special interest
ALT:	alanine transaminase
AUC:	area under the curve
CDLQI:	children dermatology life quality index
CER:	ceramides
DLQI:	dermatology life quality index
EASI:	eczema area and severity index
EOS:	E for esterified / O for omega-hydroxy / S for sphingosin
EOS CER:	highly hydrophobic omega-esterified fatty acid sphingosine ceramides
EoT:	end of treatment phase
FLG:	filaggrin
ICF:	informed consent form
IGA:	investigator global assessment
IL:	interleukin
IMP:	investigational medical product
ISS:	Individual Signs Score
ITT:	intent-to-treat
LC-MS/MS:	liquid chromatography with tandem mass spectrometry
mITT:	modified intent-to-treat
MKI67:	antigen ki-67
NRS:	numerical rating scale
NS:	non-hydroxy fatty acid sphingosine
NS CER:	non-hydroxy fatty acid sphingosine ceramides
PCA:	pyroglutamic acid, also pyrrolidone carboxylic acid
POEM:	patient oriented eczema measure

PRO: patient reported outcomes
Q2W: every second week
QOL: quality of life
SAE: serious adverse event
SC: subcutaneous
SCORAD: SCORing atopic dermatitis
STS: skin tape stripping
TEWL: transepidermal water loss
UCA: urocanic acid
ULN: upper limit of normal

1 STATISTICAL AND ANALYTICAL PROCEDURES

1.1 INTRODUCTION

The purpose of this document is to provide additional technical details.

A comprehensive and detailed description of strategy and statistical technique used to perform the analysis of data was provided in Section 9 of the protocol (amendment 01, dated 28-Jul-2020).

Adverse events will be coded according to the Medical Dictionary for Regulatory Activities (MedDRA version 24.0).

Previous and concomitant medication records will be coded according to the World Health Organization Drug Dictionary (WHO-DD version March 2021).

The definitions of potentially clinically significant abnormalities (PCSA list, BTD-009536 Version 3.0, dated 24 May 2014) used in the statistical analysis of vital signs are provided in [Section 3.1](#) (for adult healthy volunteers), [Section 3.2](#) (for adult atopic dermatitis patients) and [Section 3.3](#) (for minor participants).

1.2 MODIFICATIONS FROM THE STATISTICAL SECTION OF THE PROTOCOL

This section describes the modifications and additional statistical analyses from the protocol.

Due to unbalance between adults and adolescents atopic dermatitis (AD) patients, analyses based on age group (adult/adolescent) will only be performed for adverse event (AE) data reporting.

The study objectives are exploratory. Sample size was not based on power requirements. No multiplicity correction will be used for the tests performed as part of the statistical analyses.

Analysis population

Any participant with major deviation impacting assessment of efficacy data (except for deviations concerning AD related prohibited therapy administration) will be excluded for the modified-Intent-to-treat (mITT) population.

Demographic and medication data

Descriptive statistics for disease duration since AD diagnostic will be provided by cohort and age group (adults/adolescents).

Medications (including rescue medications) administered during the follow-up period will be summarized, in addition to previous and concomitant medications.

Efficacy analysis

Change from baseline in TEWL data is defined as change versus Day 1 TEWL data at matched number of STS samples (eg, TEWL after 5 STS at Week 16 will be compared to TEWL after 5 STS at Day 1).

Individual Signs Score (ISS) questionnaire was not done as planned per protocol. Instead, to assess lesion severity locally, Quantificare evaluation data will be used. Global Individual Signs Score (GISS) was evaluated during the study. Both Quantificare data and GISS data will be analyzed using descriptive statistics for raw data, absolute and percent by timepoints. For AD patients, on mITT population, correlation with TEWL data will be evaluated. Scatterplots will be provided to visualize the form of the relationship and Spearman's rank correlation coefficient as well as p-values at specific timepoints (Baseline, Week 8 and Week 16) will be provided.

Adverse event data

All summary of AEs will be provided by cohort and age group.

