			D4 ±2 days	D8 ±2 days	D11 ±2 days	D15 ±2 days	D22 ±2 days	D29 ±2 days	D43 ±2 days	D57 ±3 days	D85 ±3 days				
Day	D-28 to D-1	D 1												UNSCH	
Week		W0	W1			W2	W3	W4	W6	W8	W12	W16	W20		
Visits	V01	V02	V03	V04	V05	V06	V07	V08	V09	V10	V11	V12	V13		
Quality of sleep NRS ^g		X	X	X	X	X	X	X	X	X	X	X		(X)	X
Safety															
Adverse event collection	X	X	X	X	X	X	X	X	X	X	X	X	X	X	X
Height		X													
Body weight		X										X			X
Vital signs ^d	X	X								X		X		(X)	X
Physical examination	X	X ^k										X ^k			X ^k
Pregnancy test (urine), WOCBP only ^e	X	X						X		X	X	X			
DNA sampling for filaggrin gene sequencing		X													
Optional assessments															
DNA sampling for future research		X													
Biomarker research samples (serum and plasma)		X										X			X

a EoS safety follow-up by phone.

b Loading dose dupilumab arm 600 mg (300 mg x 2 ie, two 300 mg syringes) for all adult patients and for those adolescents weighing 60 kg and above, and 400 mg (200 mg x 2 ie. two 200 mg syringes) for adolescent patients below 60 kg, followed by bi-weekly SC dosing of 300 mg dupilumab to adults and adolescents weighing 60 kg and above and bi-weekly SC dosing of 200 mg to adolescents weighing below 60 kg. Dupilumab administration on following days: D1 (V02,W0) baseline, D15±2days (V06, W2), D29±2days (V08, W4), D43±2days (V09, W6), D57±3days (V10, W8), D71±3days (W10; self-administration of dupilumab at home), D85±3days V11, W12), D99±3days (W14; self-administration of dupilumab at home).

c Assessments on treatment days are to be conducted before administration of dupilumab.

d Vital signs, including systolic and diastolic blood pressure (mmHg), pulse rate (beats per minute), body temperature (°C), and respiratory rate will be measured at Screening, Baseline at Week 0, Week 8, and Week 16 (EoT). Height (cm) will be measured at Baseline only. Body weight (kg) will be measured at Baseline, and Week 16 (EoT).

e Only for women of childbearing potential. Pregnancy will lead to definitive treatment discontinuation in all cases.

f DLQI will be used for adults; CDLQI will be used for adolescents.

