2.1 STUDY RATIONALE

The objective of this study is to assess dupilumab treatment effect on skin barrier function measured by TEWL and measurement of lipids, proteins and gene expression associated with skin barrier function from skin tape stripping in patients with moderate to severe atopic dermatitis, and to evaluate the relationship between skin barrier function and disease activity measured by clinical assessments and patient reported outcomes, as well as high definition standard photography. TEWL is one of the most broadly used, non-invasive methods for measuring the function of the skin barrier. The first measurement approaches were described in 1911, and today this parameter is regarded as the standard in a variety of dermatological and skin research contexts. TEWL is influenced by many environmental and individual factors, including age, sex, race, anatomical region, skin temperature, environmental conditions, season, smoking status, measurement technique and many others (8). Therefore, including a 'normal' TEWL from an age-, gender-, targeted lesion area- and study site-matched healthy volunteers cohort assessed at the same time in the same measurement conditions on the same anatomical region with reference thresholds of skin barrier function evaluation indicating pathological relevance is important (8, 9). For this reason, an age-, gender-, targeted lesion area- and study-site-matched healthy volunteer cohort is included as a reference that could help with interpreting study results.

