9.4.7.1 Description of efficacy variables

Efficacy parameters are described in [Section 8.2](#). The derivation of baseline results is described in [Section 9.4.4.2](#).

The analysis of the efficacy marker will be based on the mITT population. As a sensitivity analysis, the primary endpoint will also be analyzed based on the ITT population. Secondary endpoints analysis might be run on the ITT population as sensitivity analysis in case an important number of patients using rescue therapy is observed.

Sub-analysis might be done for adolescents and adults, if deemed appropriate.

TEWL data collected at the same visit from without and before STS measurement on each of the three spots within the predefined skin areas will be averaged, unless a large difference between spots is observed.

Analysis

Table 4 - Efficacy analyses

Endpoint	Statistical Analysis Methods
Primary	
Percent change from baseline in TEWL after 5 STS assessed on lesional skin at Week 16 in AD patients	
Raw data and change from baseline; ie, absolute and percentage changes, will be summarized with descriptive statistics (such as mean, median, SD, minimum, and maximum) based on the mITT and ITT populations.
 
Profiles for baseline and Week 16 time points will be generated for individual values: eg, spaghetti plot and boxplot, and patients' cohort means.
 
For information purpose as study is not powered (no multiplicity correction will be applied):
 
Difference between baseline and Week 16 values will be tested through one-sided paired t-test at a Type 1 error level of alpha=0.05 ($H_0: 0 \leq TEWL_{Week16} - TEWL_{baseline}$, $H_a: 0 > TEWL_{Week16} - TEWL_{baseline}$).
 
Point estimate, two-sided 90% confidence interval and corresponding one-sided p-value will be reported.
 
If assumption of normal distribution is strongly violated, non-parametric methods: eg, Wilcoxon signed-rank test, will be used; normality assumption will be assessed through quantile-quantile plot and Shapiro-Wilk test at 5% Type I error.

Endpoint	Statistical Analysis Methods
Secondary	
Change (percent and absolute) from baseline in TEWL after 20 STS assessed on lesional skin at Week 16 in AD patients	The similar approach as for the analysis of primary endpoint will be used.

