
Correlation between baseline values of TEWL before STS and TEWL AUC in lesional and non-lesional skin of AD patients with the following baseline measures:
 
 • Local target lesion erythema and edema/papulations; ISS • EASI, SCORAD • POEM, DLQI, CDLQI, peak pruritus NRS, and quality of sleep NRS • Lipidomics in STS (ratio of EOS CER to NS CER) • FLG breakdown products of UCA and PCA concentrations in STS • Key components of skin proteomics in STS (expression of proteins associated with skin barrier function) • Key components of gene expression from transcriptomics • Image-derived severity score in targeted lesional skin 	
Scatterplot to visualize the form of the relationship between variables will be produced for patients' cohort at specific time points: ie, baseline, Week 8 and Week 16, based on the mITT population.
 
Pearson correlation will be assessed at each defined time points for EASI, SCORAD, POEM, DLQI/CDLQI, peak pruritus NRS, quality of sleep NRS, and photograph outputs. Pearson correlation coefficient and p-value will be reported.
 
Spearman's rank correlation will be assessed at each defined time points for ISS. Spearman correlation coefficient and p-value will be reported.
 
As exploratory analysis repeated measures correlation method might be used to assess the overall correlation pooling data from baseline, Week 8 and Week 16 (34).

Endpoint	Statistical Analysis Methods
Correlation between percent change from baseline in TEWL before STS and TEWL AUC in lesional and non-lesional skin of AD patients at Week 8 and Week 16 with corresponding change from baseline in the following measures:	
• Local target lesion erythema and edema/papulations; ISS• EASI, SCORAD• POEM, DLQI, CDLQI, peak pruritus NRS, and quality of sleep NRS• Lipidomics in STS (ratio of EOS CER to NS CER)• FLG breakdown products of UCA and PCA concentrations in STS• Key components of skin proteomics in STS (expression of proteins associated with skin barrier function)• Key components of gene expression from transcriptomics• Image-derived severity score in targeted lesional skin

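### The plan does not say whether the DLQI (adults) and CDLQI (adolescents) are pooled; if they are, their correlation with TEWL should be adjusted for questionnaire

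*SAP*

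**What the plan says.** Footnote f to the patients' schedule of activities (protocol 1.3) assigns the questionnaire by age: "DLQI will be used for adults; CDLQI will be used for adolescents".

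Protocol Table 4 (section 9.4.7.1) handles the two scores in two ways.

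- **Methods column.** The two are joined by a slash as one entry, once for summary statistics and mean plots in the patients' cohort, and once for the correlation with TEWL: "Pearson correlation will be assessed at each defined time points for EASI, SCORAD, POEM, DLQI/CDLQI, peak pruritus NRS", with the coefficient and p-value to be reported.
- **Endpoint column.** For the same correlations they are separate entries: "POEM, DLQI, CDLQI, peak pruritus NRS, and quality of sleep NRS". The change endpoint also divides them by age.

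On age groups, the protocol left an option open: "Sub-analysis might be done for adolescents and adults, if deemed appropriate". SAP 1.2 closes it. "Due to unbalance between adults and adolescents atopic dermatitis (AD) patients", it says, "analyses based on age group (adult/adolescent) will only be performed for adverse event (AE) data reporting". The actual split is not given. The efficacy paragraph of SAP 1.2 changes the handling of the ISS but does not mention the DLQI or CDLQI. Neither document specifies adjustment for age group or questionnaire, and SAP 1.2 rules out multiplicity correction.

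Protocol 2.1 adds that "TEWL is influenced by many environmental and individual factors, including age".

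**The concern.** Age group decides which questionnaire a patient completes and, on the protocol's own account, age also affects TEWL. A single Pearson coefficient across all patients therefore mixes two things: the association among patients who answered the same questionnaire, and the gap between adults and adolescents. With a gap in both variables, the coefficient can be non-zero when there is no association in either group. If the gap runs against a real association, it can hide it.

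Exploring how barrier function relates to patient-reported burden is a stated tertiary objective, and a p-value will accompany each coefficient. A reader could take a difference between age groups or questionnaires for a link between skin barrier and quality of life. Pooled means and mean plots have a related weakness: they average two instruments in proportions set by the age mix.

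**Working it through.** **The plan's own figure.** The only sizing figure is enrolment: 20 evaluable patients with 15% drop-out gives 20/0.85 = 23.5, rounded up to 24, as protocol 9.2 states. The documents give no figure for the DLQI/CDLQI correlation.

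**Which reading the text supports.** If the methods column is followed literally, the scores are pooled with no adjustment. If the endpoint column is followed, there is one correlation in adults and one in adolescents, which is in effect an age-group efficacy analysis, and SAP 1.2 confines age-group analyses to adverse events. Pooling is thus the likelier reading, but it remains an inference.

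**Inputs for the pooled case**
- Split: about 10 adolescents and 10 adults, at most 12 of either (protocol synopsis). A 15/5 split exceeds that cap; it is shown because the SAP reports imbalance.
- Differences d1 (TEWL) and d2 (score) between age groups, in within-group SDs: assumed, since the documents give none.
- Correlation within each age group: set to 0.
- Test level: two-sided 5%, assumed, since none is stated for the correlations.

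**Formula.** With adolescent share p and v = p(1 − p),

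r = v·d1·d2 / √[(1 + v·d1²)(1 + v·d2²)].

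For a 10/10 split, v = 0.25. At d1 = d2 = 0.5: 0.0625/1.0625 = 0.06. At 1: 0.25/1.25 = 0.20. At 1.5: 0.5625/1.5625 = 0.36. If either difference is 0, the numerator and r are 0. Opposite signs give the same size with a minus sign.

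**False-positive rates** come from simulation (40,000 runs, normal data). The adjusted column uses values centred within questionnaire, with n − 3 degrees of freedom.

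| Split | d1, d2 (SD) | Pooled r | Pooled rejections | Adjusted rejections |
|---|---|---|---|---|
| 10/10 | 0, 1 | 0 | 5.0% | 5.0% |
| 10/10 | 0.5, 0.5 | 0.06 | 5.6% | 5.0% |
| 10/10 | 0.8, 0.8 | 0.14 | 8.7% | 4.9% |
| 10/10 | 1, 1 | 0.20 | 13.9% | 4.9% |
| 10/10 | 1.5, 1.5 | 0.36 | 37.8% | 5.0% |
| 12/8 | 1, 1 | 0.19 | 13.3% | 5.2% |
| 12/12 | 1, 1 | 0.20 | 15.7% | 5.0% |
| 15/5 | 1, 1 | 0.16 | 10.1% | 4.9% |

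Across all scenarios run, the adjusted rate stayed between 4.8% and 5.3%.

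**Cost of each remedy at n = 20.** The pooled coefficient reaches p < 0.05 at |r| above 0.44. The partial correlation has 17 degrees of freedom (t = 2.110) and needs 2.110/√(17 + 2.110²) = 0.46. Separate correlations need 0.63 with 10 patients and 0.88 with 5.

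**Levels and changes.** The baseline correlation uses levels, where a lasting age difference enters directly. The Week 8 and Week 16 change correlations use percent change in TEWL and change in score. A stable difference in level does not by itself create a difference in those changes, so there d1 and d2 must be differences in the changes themselves.

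**The case against.** The strongest reply is that pooling is nowhere stated. The endpoint column separates the two scores, and the slash may be shorthand for two instruments, as in the schedule of activities, where the footnote assigns one to each age group. The SAP sentence reads most naturally as withdrawing the optional subgroup analysis. Nor is its restriction applied literally: the same section summarises disease duration by age group. Reporting two named endpoints need not count as an age-group analysis. This stands as a reason not to assert pooling. It does not settle what the analyst should do.

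The size is also open. Protocol 8.2.9 presents the CDLQI as the validated counterpart of the DLQI, though it does not say that the scores are interchangeable. Protocol 2.1 gives neither size nor direction for the effect of age on TEWL. At 0.5 SD the artefact is negligible. The age mechanism could also affect the other severity and PRO correlations; only the change of questionnaire is specific to this pair. Scatterplots are planned, and the repeated measures correlation, which works within patients, would remove a constant age gap, but it is only optional.

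A reader might infer that a patient who turns 18 during the study will switch instrument and so produce a meaningless change score. The documents do not support this: no passage describes a switch, the text is silent on when age is fixed for this purpose, and any probability depends on an assumed age distribution.

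**Conclusion.** The point holds as a cheap improvement to a tertiary/exploratory analysis. Questionnaire and age group cannot be separated by design, the methods and endpoint columns of Table 4 point different ways, and SAP 1.2 makes the unadjusted pooled analysis the likelier outcome without saying so.

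If the scores are pooled, the distortion ranges from negligible to material: with a 10/10 split, r from 0.06 to 0.36 and a false-positive rate from 5.6% to 37.8% for equal differences of 0.5 to 1.5 SD. These results rest on assumed differences in both variables, normal data, no correlation within groups and a two-sided 5% level. The concern is clearest at baseline.

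A reader might go further and conclude that the plan prescribes a biased correlation, or that any association found will be spurious. Neither follows: pooling is inferred, and the artefact vanishes if either TEWL or the score does not differ by age group. The primary endpoint does not use these questionnaires and is unaffected.

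**What to change.** 1. State in SAP 1.2 that the age-group restriction does not apply to the DLQI and CDLQI, so that it agrees with both columns of Table 4.
2. Summarise and plot the DLQI in adults and the CDLQI in adolescents separately.
3. Replace the pooled Pearson coefficient with a partial correlation between TEWL and score, adjusted for questionnaire and using all patients, at baseline and for the Week 8 and Week 16 changes.
4. Mark the planned scatterplots by questionnaire.

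No new data are needed. The correlation loses one degree of freedom, and each descriptive summary has fewer patients. The partial correlation removes the gap in level between groups but assumes a similar association within each; the marked scatterplots let a reader judge that. Fully separate correlations would also remove the artefact but, at these numbers, would detect only strong associations, so they are not the recommended replacement.

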Lesional and non-lesional skin areas for TEWL assessment and STS will be identified on the upper limbs or lower limbs at baseline ("predefined skin area"). TEWL and STS-assessment at pre-defined non-lesional (normal looking) skin area in AD patients should be made about 4 cm from the edge of the lesional area.

Within the predefined lesional skin (LS) and non-lesional skin (non-LS) areas three closely adjacent spots will be identified for subsequent skin barrier function assessment (3 spots on lesional skin, 3 spots on non-lesional skin). These spots must not overlap with each other once skin tapes are applied.

The skin barrier function without and before STS will be assessed using TEWL measurement on each of the three spots within these pre-defined skin areas at each visit.

Repeated TEWL assessment in pre-defined lesional and non-lesional skin areas of AD patients after STS for lipidomics, proteomics and transcriptomics analysis in STS samples will be conducted at baseline (Week 0, Day 1), Week 2 (Day 15), Week 4 (Day 29), Week 8 (Day 57), Week, 12 (Day 85), and at EoT at Week 16 (Day 113).

In order to allow the skin to recover from the STS, the skin barrier function assessment with STS will be performed as follows: STS assessment on baseline (Week 0), Week 8 and Week 16 will be conducted on the first spot within the predefined lesional and non-lesional skin area. STS assessment on Week 2 will be conducted on the second spot. STS assessment on Week 4 and Week 12 will be conducted on the third spot.

TEWL will be measured before and after 5, 10, 15, and 20 STS (5 TEWL assessments per visit) on targeted, predefined lesional, non-lesional skin in AD patients at baseline, Week 2, Week 4, Week 8, Week 12, and Week 16 on the predefined first, second or third spot, respectively.

Skin barrier function in approximately twenty healthy volunteers matched for age, gender, location of targeted lesion area, and study site to the AD cases will be assessed in a similar manner at baseline, twice a week during the first two weeks, once a week during Week 3 to Week 4, every two weeks from Week 4 to Week 8, and every four weeks up to Week 16 thereafter, serving as a reference comparator for skin barrier function.

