- g* Peak pruritus NRS and quality of sleep NRS will be assessed daily from Day-7 to Day -1; daily from Day 1 to Day 29 and then for the 7 days prior to Week 6, Week 8, to Week 12 and to Week 16 by e-diary. Patients will bring the eDiary to the site at each visit. eDiary will be reviewed for any questionnaires omission and dispensed back to patients at each visit.
- h* TEWL to be conducted before STS and then after 5, 10, 15, and 20 STS in pre-defined lesional and non-lesional skin. All skin tape strips will be collected and stored.
- i* At Week 0, 8 and 16 STS will be conducted on the first spot within the predefined skin area. At Week 2 STS will be conducted on the second spot within the predefined skin area. At Week 4 and 12 STS will be conducted on the third spot within the predefined skin area. TEWL will be assessed in lesional and non-lesional skin before STS and after 5, 10, 15, and 20 STS. All skin tape strips will be collected and stored for lipidomics, proteomics, and transcriptomics analyses.
- j* Emollients should NOT be applied from Day -7 to the EoT (Week 16, Day 113) to the targeted, pre-defined skin areas that will be used for TEWL assessment. Participants should not take showers or soaking in a bathtub within 6 hours before TEWL assessment. Compliance must be documented in participant's source data. Emollients for use during the study will be provided by the study site to study participants. Use of emollients should be documented in a diary.
- k* Limited to skin-related physical examination at baseline and EoT visit.
- l* Pre-defined lesional (3 spots) and non-lesional skin areas (3 spots), whereby the assessment spots on non-lesional skin are located about 4 cm apart from the edge of the AD lesion.
- m* TEWL will be measured at each of the three closely adjacent spots within the predefined skin areas at all visits as baseline assessment; if there is STS, subsequent TEWL assessment will only be done at the lesional and no-lesional spot, at which STS is performed.
- n* In case STS assessment is to be conducted at an unscheduled visit or at a premature end of treatment visit the assessment should be conducted at that spot of the skin area, for which the period passed since the last STS assessment is the longest.

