8.2 EFFICACY ASSESSMENTS

8.2.1 Transepidermal water loss assessment and skin tape stripping

8.2.1.1 Transepidermal water loss assessment

Transepidermal water loss is a skin barrier function test that measures perspiration or water loss through the skin. Transepidermal water loss is generally higher in AD skin compared to normal skin as the barrier is disrupted allowing water to evaporate more readily. If the barrier improves with dupilumab treatment, TEWL would be expected to decrease.

TEWL assessment will be conducted in a quiet environment with temperature and humidity being documented. TEWL measurements will be conducted in the same room throughout the study where possible. Subjects will be acclimated to the room for a minimum of 20 minutes prior to TEWL measurements. Room temperature will be set to be within 19.0°C to 23.0°C. Humidity will be set to be below 60% as the maximum allowed humidity. To further control TEWL readout, moisturizers will be standardized for all study participants starting from Day -7 until Day 113 (Week 16). The first TEWL assessment at each visit will be conducted at each of the three spots in predefined lesional and non-lesional areas respectively. After start of STS all subsequent TEWL assessments at each visit will be done on the single lesional and non-lesional spot respectively at which the STS is performed (see also [Figure 3](#)).

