Change (percent and absolute) from baseline in TEWL after STS assessed on lesional skin in AD patients over time	As exploratory analysis time to improvement of skin barrier function for lesional and non-lesional skin area measured by TEWL will be summarized. Improvement is defined as time to the first post-baseline day for which at least one TEWL measure of a patient is equal or lower than the median, of the corresponding TEWL measured in his/her matched healthy volunteer over time. Results might be reported through Kaplan-Meier plot.
Change (percent and absolute) from baseline in TEWL after STS assessed on non-lesional skin in AD patients over time	
Change (percent and absolute) from baseline in TEWL after STS assessed on normal skin in healthy volunteers over time	
Change (percent and absolute) in TEWL area under the curve (TEWL AUC: a composite measure before and after 5, 10, 15 and 20 STS) for skin barrier function in lesional skin in AD patients over time	As all TEWL values are expected to be positive, area under the TEWL curve will be calculated using the trapezoidal method over the 10 or 20 STS (measurement at every five STS) at each visit.
Change (percent and absolute) in TEWL area under the curve (TEWL AUC: a composite measure before and after 5, 10, 15, and 20 STS) for skin barrier function in non-lesional skin in AD patients over time	Raw data and change from baseline; ie, absolute and percentage changes, will be summarized with descriptive statistics (such as mean, median, SD, minimum, and maximum) by groups and time points.
Change (percent and absolute) in TEWL area under the curve (TEWL AUC: a composite measure before and after 5, 10, 15, and 20 STS) for skin barrier function in normal skin in healthy volunteers over time	Profiles over study days will be generated for individual values and group means for raw data and absolute change from baseline.
	Percentage change relative to the healthy volunteers' cohort will be calculated as a ratio of means by time point for lesional and non-lesional skins groups.
	As exploratory analysis time to improvement of skin barrier function for lesional and non-lesional skin area measured by TEWL AUC will be summarized. Improvement is defined as time to the first post-baseline day for which TEWL AUC of a patient is equal or lower than the median, of the corresponding TEWL AUC computed in his/her matched healthy volunteer over time. Results might be reported through Kaplan-Meier plot.
Tertiary/exploratory	

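### After-STS changes at Weeks 2, 4 and 12 are taken against a Day 1 value from a different spot, and the collected data can adjust for this only in part

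*SAP*

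**What the plan says.** The SAP (1.2, Efficacy analysis) defines change as follows: "Change from baseline in TEWL data is defined as change versus Day 1 TEWL data at matched number of STS samples". Spot is not mentioned.

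The protocol synopsis fixes the rotation. Three visits share one spot: "STS assessment on baseline (Week 0), Week 8 and Week 16 will be conducted on the first spot". The first visit after baseline moves to another: "STS assessment on Week 2 will be conducted on the second spot". The two visits that are left use the last one: "STS assessment on Week 4 and Week 12 will be conducted on the third spot". Healthy volunteers follow the same rotation. Protocol 8.2.1.2 gives the reason, which is to let the skin recover by spacing strippings of one spot 8 weeks apart.

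Where TEWL is measured depends on whether stripping has begun. Before stripping, all spots are read: "The first TEWL assessment at each visit will be conducted at each of the three spots in predefined lesional and non-lesional areas respectively". After that, the schedule of activities for AD patients states: "if there is STS, subsequent TEWL assessment will only be done at the lesional and no-lesional spot, at which STS is performed".

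The affected secondary endpoints in protocol Table 4 include "Change (percent and absolute) from baseline in TEWL after STS assessed on lesional skin in AD patients over time", its non-lesional and healthy-volunteer counterparts, and TEWL AUC over time.

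Protocol 9.4.4.2 and 9.4.7.1 average the three unstripped readings, except where the spots differ widely (no cut-off is given). Neither document plans a spot-specific baseline, a spot term or a cross-spot label for after-STS values. SAP 1.3 imputes missing TEWL by LOCF and has no rule about spot.

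**The concern.** The second secondary objective is the time course of barrier function before and after stripping. At Weeks 2, 4 and 12 the after-STS change combines the change over time with whatever difference exists between two spots of the same area. Stripping history also shifts along the course, from skin not stripped before to skin stripped twice. Someone reading the planned profiles could take a step between visits for treatment kinetics when part of it comes from the spot used. The extra scatter also widens the spread of individual changes at these visits, in about 20 evaluable patients.

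**Working it through.** **Plan's own figures.** The documents give no between-spot or within-spot SD. The only sample-size arithmetic, 24 enrolled for 20 evaluable at 15% drop-out, reproduces (20/0.85 = 23.5, rounded up to 24) but does not bear on this point.

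**Step 1: spot by visit**, from the protocol synopsis and schedules.

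| Visit | Spot stripped | Day 1 after-STS value on that spot? | Earlier strippings of that spot |
|---|---|---|---|
| Day 1 | 1 | yes (baseline) | 0 |
| Week 2 | 2 | no | 0 |
| Week 4 | 3 | no | 0 |
| Week 8 | 1 | yes | 1 |
| Week 12 | 3 | no | 1 |
| Week 16 | 1 | yes | 2 |

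Three of the five post-baseline visits are cross-spot. Weeks 8 and 16 are same-spot.

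**Step 2: noise.** Let sw be the within-spot visit-to-visit SD and ss the between-spot SD, with independent components.

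- Same spot: Var(change) = 2·sw².
- Different spots: Var(change) = 2·sw² + 2·ss².
- SD ratio = √(1 + r²), where r = ss/sw.

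For assumed r:

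- r = 0.25: √1.0625 = 1.03, up 3%
- r = 0.5: √1.25 = 1.12, up 12%
- r = 1.0: √2 = 1.41, up 41%

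**Step 3: what adjustment can recover.** Day 1 unstripped TEWL exists for every spot: it "will be assessed using TEWL measurement on each of the three spots within these pre-defined skin areas at each visit". Suppose unstripped spot differences correlate c with after-STS spot differences and are measured with reliability q. Adjustment then removes a share c²·q of the spot term, leaving an SD ratio of √(1 + r²(1 − c²q)). Both c and q are assumptions.

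| r | No adjustment | c = 0.5, q = 0.7 (share 0.175) | c = 0.8, q = 0.9 (share 0.576) | c = q = 1 |
|---|---|---|---|---|
| 0.25 | 1.03 | 1.03 | 1.01 | 1.00 |
| 0.5 | 1.12 | 1.10 | 1.05 | 1.00 |
| 1.0 | 1.41 | 1.35 | 1.19 | 1.00 |

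The inflation disappears only if unstripped differences predict after-STS differences perfectly and without error.

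**Step 4: bias, only if numbering is systematic.** Assume a true change of −40% and a spot that averages 10% above or below spot 1. The cross-spot result is 0.60 × 1.10 − 1 = −34%, or 0.60 × 0.90 − 1 = −46%, which is 6 points off either way. If the unstripped ratio captures half of the log spot difference, 0.60 × √1.10 − 1 = −37.1% and 0.60 × √0.90 − 1 = −43.1%, about 3 points off. If numbering is haphazard across patients, the expected mean spot difference is zero and only Step 2 applies.

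**Step 5: LOCF.** If Week 16 is missing and Week 12 is present, LOCF sets a spot 3 value against a spot 1 baseline in the primary endpoint. If Week 8 is missing and Week 4 is present, the same happens at Week 8.

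**The case against.** The rotation is a deliberate design choice, the spots are closely adjacent, and the over-time endpoints are summarised descriptively in a study not sized for power. Healthy volunteers follow the same rotation and strip counts, and results are expressed relative to them by visit and strip count, which is a partial reference for any systematic effect of spot number or stripping history. The unstripped time course averages all three spots throughout, so the rotation does not touch it. The Week 8 and Week 16 correlations use same-spot values when observed. All of this stands, and it keeps the point small. The volunteer ratio does not capture heterogeneity within a patient's lesion, however, and protocol 3.1 itself expects disrupted skin to react more to stripping than healthy skin.

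Three stronger readings are tempting, and the documents do not support them:

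- A reader might infer that data already collected could remove the spot differences. Spots 2 and 3 are not stripped on Day 1, so their after-STS baseline does not exist. Protocol 3.1 also treats undisturbed TEWL and TEWL under stripping as measuring different properties.
- A reader might infer that the mean time course is biased. That needs systematic spot numbering, and the documents do not say how spots are numbered.
- A reader might infer that a mixed model would separate treatment from spot and stripping history. Every participant has the same rotation, so spot number and earlier strippings are fixed by visit. Apart from what the unstripped covariate explains, they cannot be told apart from visit.

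On LOCF, SAP 1.3 introduces its rules as applying where the protocol's statistical section does not say otherwise, and protocol 9.4.7 says missing efficacy data are not imputed, apart from rescue-related values. Step 5 reads the explicit SAP rule on missing TEWL as the one that will be used.

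**Conclusion.** The point holds as a modest one about precision and reading. Changes in after-STS TEWL and TEWL AUC at Weeks 2, 4 and 12 are cross-spot, and nothing in the plan labels or adjusts for it. The size is unknown. The 3%, 12% and 41% figures rest on assumed variance ratios, and the last needs adjacent spots to differ as much as one spot varies between visits. How much an adjustment recovers is also assumed.

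The primary endpoint and the other Week 16 after-STS endpoints compare spot 1 with spot 1 when observed. It would go too far to call them unaffected without qualification, because an imputed Week 16 value can come from spot 3. It would equally go too far to call the primary endpoint compromised, since only patients with an imputed value are touched.

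**What to change.** Keep the planned unadjusted summaries and add the following to the SAP:

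- In the time-course tables and plots, mark Weeks 2, 4 and 12 as cross-spot and give the number of earlier strippings of the spot used.
- Show the same-spot course (Day 1, Week 8, Week 16) separately.
- Add a supplementary analysis of after-STS TEWL, for example on the log scale, adjusting for each spot's own Day 1 unstripped TEWL. State that the adjustment is partial and that systematic effects of spot number and stripping history cannot be separated from visit.
- For LOCF of after-STS TEWL, carry forward only from the same spot, for example Week 8 to Week 16 and Week 4 to Week 12. Say what happens where no useful donor exists: Weeks 2 and 4 have no earlier same-spot value, and Week 8 has only Day 1, which would set the change to zero.

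All the data needed are already scheduled. The cost is SAP wording and one extra analysis with added model assumptions in about 20 patients. Same-spot LOCF also carries forward an older value, 8 weeks back for Week 16 instead of 4.
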